Transcranial alternating current brain stimulation (tACS), is a neurophysiological method of non-invasive modulation of the excitability of the central nervous system that is having an increasingly numerous spectrum of potential therapeutic applications. Recent studies have demonstrated the effectiveness of this method in modulating the natural frequencies of cerebral oscillation, underlying multiple cognitive processes such as verbal memory, perception and working memory.

On the basis of these premises, the treatment with gamma tACS is proposed in patients affected by Alzheimer's disease.

In this randomized, double-blind, sham-controlled, cross-over study, the investigators will evaluate whether a single stimulation with gamma tACS on the posterior parietal cortex can improve symptoms in patients with Mild Cognitive Impairment due to Alzheimer's disease.

Presidio Ospedaliero
di Brescia

Sistema Socio Sanitario

Regione
Lombardia

ASST Spedali Civili

Università
degli Studi
di Brescia

CLINICA NEUROLOGICA - UNIVERSITA' DEGLI STUDI DI BRESCIA
UO Neurologia 2 - AZIENDA SOCIO SANITARIA TERRITORIALE degli SPEDALI CIVILI DI BRESCIA
Direttore: [name]

Subjects will be randomized in two groups, one receiving a single treatment with gamma tACS (40 Hz) first and the other receiving sham stimulation. After one week the treatments will be exchanged. Patients will be evaluated with neuropsychological tests and neurophysiological measures of cholinergic transmission.

OBJECTIVES: The aim of the study is to evaluate the effects on cognitive performance of tACS in patients suffering from Alzheimer's disease (AD) to identify a possible rehabilitation protocol. The effect of tACS on intracortical connectivity will also be evaluated using the and SAI TMS protocols.

PROCEDURES: Patients followed at the Neurological Clinic with a diagnosis of Alzheimer's disease will be enrolled according to current clinical criteria. Patients will be randomized into two groups:

The first group will undergo a stimulation protocol by means of tACS (real), the second group will undergo a placebo treatment (sham).

Treatment group:

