Each session will consist in the application of a tACS session (real at 3 mA) at the cortical level for the duration of 60 minutes each, during which patients will be subjected to an experimental cognitive task (Face Naming Task). The pre- and post-stimulation effects with tACS will be evaluated; in particular, the effects on cognitive performance will be assessed through the use of dedicated tests (Rey Auditory Verbal Learning Test - RAVLT) and the effects on the neurophysiological parameters of SAI using TMS.

Placebo group:

In the placebo group, the assembly will be kept the same as that of the real stimulation, however the electric current will be automatically interrupted about 5 seconds after the start of the stimulation, so as to make the placebo stimulation indistinguishable from the real one. The same tests and assessments used during real stimulation will be used.

After 1 week (after a single session of real stimulation or placebo stimulation) the two groups will be inverted (cross over).

INCLUSION CRITERIA:

- Mild Cognitive Impairment due to Alzheimer's disease (according to Albert et al., *Alzheimers Dement* 2011).

Presidio Ospedaliero
di Brescia

Sistema Socio Sanitario

Regione
Lombardia

ASST Spedali Civili

Università
degli Studi
di Brescia

CLINICA NEUROLOGICA - UNIVERSITA' DEGLI STUDI DI BRESCIA
UO Neurologia 2 - AZIENDA SOCIO SANITARIA TERRITORIALE degli SPEDALI CIVILI DI BRESCIA
Direttore: [name]

EXCLUSION CRITERIA:

- Cerebrovascular disorders, previous stroke, hydrocephalus, and intra-cranial mass documented by MRI.
- History of traumatic brain injury or other neurological diseases.
- Serious medical illness other than FTD
- History of seizures
- Pregnancy
- Metal implants in the head (except dental fillings)
- Electronic implants (i.e. pace-maker, implanted medical pump)
- Age <18 years

STUDY DESIGN: this is a placebo-controlled, randomized, double-blind, non-pharmacological interventional clinical trial, as neither the patients nor the person who will administer the evaluation tests will be aware of the type of treatment performed, real-tACS or placebo (tACS: placebo tACS = 1 : 1). This is a crossover study, in fact the patients who will carry out the first real stimulation session will carry out a second session with placebo stimulation after 1 week and vice versa. An experimental task (Face Naming Task) will be performed in both sessions.

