In consideration of the transient effects of tACS, with a duration of cognitive effects of a few hours after the interruption of stimulation, the study does not provide a long-term follow-up.

Patients diagnosed with Alzheimer's Disease will be included. Each patient will undergo a cognitive assessment with the administration of a dedicated test (Rey Auditory Verbal Learning Test - RAVLT) and analysis of neurophysiological parameters of SAI by TMS before treatment and immediately after. All measures will be repeated after a week by reversing the stimulation from real to placebo and vice versa. In both sessions, a task, the Face Naming Task, will be carried out during the stimulation with tACS, both real and placebo.

END POINTS: The effect of tACS alternating current brain stimulation on the Face Naming Task and RAVLT will be primary outcome measures. The effect of tCAS on SAI measures will be considered as secondary outcome measure.

STATISTICAL PLAN: we will use parametric analyzes (t test) to compare the demographic variables (age and education) of the two groups at baseline. A $p < 0.05$ will be considered significant. To evaluate the effect of the stimulation protocol using tACS on cognitive performance we will use an ANOVA model.

Power analysis: considering that similar studies have not been published, we used data from slightly different studies (both by population and by method of stimulation),

Presidio Ospedaliero
di Brescia

Sistema Socio Sanitario

Regione
Lombardia

ASST Spedali Civili

Università
degli Studi
di Brescia

CLINICA NEUROLOGICA - UNIVERSITA' DEGLI STUDI DI BRESCIA
UO Neurologia 2 - AZIENDA SOCIO SANITARIA TERRITORIALE degli SPEDALI CIVILI DI BRESCIA
Direttore: [name]

always remaining within the established safety limits (Antal 2017). The "effect size" $f(V)$ was calculated using the direct method. Taking into consideration from the aforementioned studies an effect size equal to a partial η^2 of 0.205, equal to an "effect size" $f(V)$ of 0.5078 and, considering $\alpha = 0.05$ and the power $(1-\beta) = 0.80$, the expected sample size is 18 subjects using a repeated measures ANOVA study with two within-subjects factors: both treatment (real vs placebo - crossover study) and time (T0 and T1). The proposed sample size of 20 subjects should be adequate to achieve the main objective of the study.

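### Two primary outcomes, one unsplit 0.05 and no success rule: if either may be claimed, the chance of a false primary claim is about 7% to 10% with one test per outcome

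*Combined protocol and SAP*

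**What the plan says.** All references are to the combined protocol and SAP.

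- **END POINTS** makes two measures primary: the effects of stimulation "on the Face Naming Task and RAVLT will be primary outcome measures". SAI is secondary. The plan therefore ranks outcomes, but does not rank these two against each other.
- **STATISTICAL PLAN** gives the efficacy analysis in one sentence: "To evaluate the effect of the stimulation protocol using tACS on cognitive performance we will use an ANOVA model". It names no RAVLT score, no Face Naming score and no ANOVA effect as decisive.
- The only significance threshold is "A $p < 0.05$ will be considered significant". It directly follows the t tests on baseline demographics.
- **Power analysis** uses a single alpha of 0.05, power 0.80 and partial eta squared 0.205, and concludes that "the expected sample size is 18 subjects using a repeated measures ANOVA study with two within-subjects factors", namely treatment and time (T0, T1). Twenty subjects are planned. The effect size is not tied to either primary outcome.
- **Timing.** In STUDY DESIGN, the sentence on the RAVLT assessment goes on to "analysis of neurophysiological parameters of SAI by TMS before treatment and immediately after", so RAVLT has a T0 and a T1. Face Naming is placed elsewhere: "In both sessions, a task, the Face Naming Task, will be carried out during the stimulation with tACS, both real and placebo". PROCEDURES agrees, describing the session as one "during which patients will be subjected to an experimental cognitive task (Face Naming Task". No T0 or T1 is described for it.
- **OBJECTIVES** is general: "The aim of the study is to evaluate the effects on cognitive performance of tACS". The hypothesis under ETHICAL CONSIDERATIONS concerns naming, but does not make naming the sole or first primary.

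**The concern.** With two primaries and no stated rule, at least four positions could be defended once the data are seen: either outcome suffices, both are needed, naming comes first, or one outcome is the real primary. They carry different false-positive rates. Under the first, the chance of at least one false primary claim is above the 5% used to size the trial. Under the others it is not, provided the choice was made in advance. What is at stake is how far a reader can trust a positive result on one outcome when the other is negative, and a rule written after unblinding cannot restore that trust.

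**Working it through.** **Inputs.** Two primary outcomes (END POINTS). Alpha 0.05, power 0.80, partial eta squared 0.205, f(V) 0.5078, required N 18, planned N 20 (Power analysis). The documents give no correlation between the two tests, so a range is assumed.

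**Step 1: reproduce the plan's own figures.** f(V) = sqrt(0.205 / 0.795) = 0.5078, as stated. For the sample size, use a noncentral F with four measurements, two sequence groups and sphericity: df1 = 3, df2 = 3(N − 2), lambda = f(V)² × 3(N − 2).

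- N = 17: power 0.789.
- N = 18: lambda = 0.2579 × 48 = 12.38, power 0.819. This reproduces 18.
- N = 20: lambda = 0.2579 × 54 = 13.93, power 0.869 at alpha 0.05 and 0.795 at alpha 0.025.
- At alpha 0.025, 80% power needs N = 21 (0.822).

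The one-group version of this formula gives 17, so it is not used. A 1-df setting with two measurements, with f treated as Cohen's f at zero correlation, also returns 18 (power at N = 20: 0.861 at 0.05 and 0.775 at 0.025), but it does not match the four-measurement design described.

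**Step 2: familywise error if either outcome may be claimed at 0.05, one test each, both nulls true.**

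Independent tests: 1 − 0.95² = 0.0975. Bound under any dependence: 0.05 + 0.05 = 0.10. For correlated two-sided tests, the error is 1 − P(|Z1| < 1.96 and |Z2| < 1.96) under a bivariate normal. The Holm column is P(either p < 0.025).

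| Assumed correlation of the tests | Either at 0.05 | Holm |
|---|---|---|
| 0 | 0.0975 | 0.0494 |
| 0.3 | 0.0951 | 0.0484 |
| 0.5 | 0.0907 | 0.0465 |
| 0.7 | 0.0835 | 0.0430 |
| 0.9 | 0.0704 | 0.0362 |

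**Step 3: more than one test per outcome.** The 10% bound no longer holds. One extra independent test, such as a second RAVLT score, gives 1 − 0.95³ = 0.143.

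**Step 4: both outcomes required at 0.05.** A false claim needs at least one true null to be rejected at 0.05, so the error is at most 5%.

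**Step 5: power at N = 20 under each rule, using the calculation from Step 1.**

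- Holm: an outcome succeeds if its p < 0.025, or if its p lies between 0.025 and 0.05 and the other outcome's p < 0.025. Its power therefore lies between 0.795 and 0.869. With equal power and independence it is 0.795 + (0.869 − 0.795) × 0.795 = 0.854.
- Both required: 0.869² = 0.756 with equal power and independence.

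These figures describe RAVLT at best. Applying them to Face Naming is illustrative, because the T0/T1 model does not describe a task done during stimulation.

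**The case against.** The strongest reply is that the plan never says either outcome suffices. END POINTS joins the two with a conjunction, and if both must succeed the error is at most 5% and no split is needed. This stands as a possible reading, and it is why the inflation is conditional. It is not settled by the text: listing two primary measures together is not a rule that both must be significant.

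Second, the 0.05 threshold is written beside the baseline t tests, so applying it to each primary ANOVA is an inference. That is fair. The alpha of 0.05 in the power calculation is the firmer support for it.

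Third, two cognitive outcomes in the same patients are plausibly positively correlated, so 9.75% belongs at the top of a range. That is accepted, and the range is given. Even at 0.9 the error is 7.0%.

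Fourth, this is a 20-patient, single-session crossover looking for a possible rehabilitation protocol, so a false positive costs less than in a large confirmatory trial. That limits how much weight the point deserves. It does not remove it: the plan names primary outcomes and sizes the trial at 80% power for a main objective.

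A reader might also take the naming hypothesis under ETHICAL CONSIDERATIONS as making Face Naming the sole primary. END POINTS contradicts that by naming both.

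**Conclusion.** The concern holds in conditional form. The plan has two primary outcomes, a single unsplit 0.05 and no success rule. If either may be claimed at 0.05, the familywise error is 7.0% to 9.75% for assumed correlations from 0.9 to 0, and at most 10% under any dependence. If both are required it is at most 5%. The first set of figures assumes one score and one ANOVA effect per outcome; the correlated values also assume two-sided tests and a normal approximation.

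Three stronger statements are tempting, and the documents do not support them:

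- That the trial runs at nearly 10% error. This needs the either-suffices reading, which the plan neither adopts nor excludes.
- That 10% is a firm ceiling. It is one only with a single decisive test per outcome, and the plan names neither the score nor the effect.
- That multiplicity makes the sample size inadequate. The loss under Holm is modest in the calculation that reproduces 18. Whether that 3-df calculation matches the effect actually tested is a separate question.

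This is a gap that should be closed before unblinding. It is not a flaw that invalidates the design.

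**What to change.** Before unblinding, add to the STATISTICAL PLAN:

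1. One RAVLT score, one Face Naming score, and the single ANOVA effect that is decisive for each.
2. A success rule. Suggested: Holm, with the smaller p tested against 0.025 and, if that is significant, the other against 0.05. This holds the familywise error at 5% under any dependence. Acceptable alternatives, if stated in writing before unblinding, are requiring both at 0.05; a fixed order, each at 0.05, with the second tested only if the first is significant; or a single primary with the other made secondary.
3. Power at N = 20 restated for the chosen rule and effect, separately for RAVLT and for Face Naming, whose measurement schedule the present model does not describe.

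**Cost.** Wording only, with no extra patients or visits. In the two-group 3-df calculation, Holm lowers power per outcome from 0.869 to somewhere between 0.795 and 0.869. Requiring both is not free either: about 0.756 with equal power and independence. A fixed order keeps 0.869 for the first outcome; under the same assumptions the second is claimed with probability of about 0.756. A single primary keeps 0.869 but gives up a primary claim on the other outcome. All figures for Face Naming are illustrative.

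### The efficacy ANOVA names no period term; stating one protects the Face Naming Task comparison at little cost

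*Combined protocol and SAP*

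**What the plan says.** The opening summary of the combined protocol and SAP sets up a two-period crossover with randomised order: "Subjects will be randomized in two groups, one receiving a single treatment with gamma tACS (40 Hz) first and the other receiving sham stimulation". The treatments are exchanged after one week. STUDY DESIGN gives the ratio as "real-tACS or placebo (tACS: placebo tACS = 1 : 1" and describes no method of randomisation.

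Under END POINTS, "The effect of tACS alternating current brain stimulation on the Face Naming Task and RAVLT will be primary outcome measures". The two are measured differently. RAVLT is given before and immediately after stimulation in each session. For the Face Naming Task, STUDY DESIGN says: "In both sessions, a task, the Face Naming Task, will be carried out during the stimulation with tACS, both real and placebo". PROCEDURES agrees, and no T0 measurement of this task is described. STUDY DESIGN adds: "All measures will be repeated after a week by reversing the stimulation from real to placebo and vice versa".

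The efficacy analysis under STATISTICAL PLAN is one sentence without factors: "To evaluate the effect of the stimulation protocol using tACS on cognitive performance we will use an ANOVA model". Factors appear only in the power analysis, which assumes a repeated measures ANOVA "with two within-subjects factors: both treatment (real vs placebo - crossover study) and time (T0 and T1"). Period, session, order and sequence are not named as model terms. In the statistical plan the two groups are used only for a baseline t test of age and education.

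**The concern.** In a two-period crossover each patient's real-minus-sham difference contains the change from session 1 to session 2. The change enters with a minus sign for patients who get real stimulation first and a plus sign for those who get sham first. Without a period term this known, removable structure is treated as random variation between patients.

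The Face Naming Task is most exposed. It is a primary outcome repeated after a week, when familiarity with the task could plausibly move the score. With no T0 described, nothing within a session cancels the shift, and the treatment by time layout of the power paragraph does not fit the task. At stake are power and interval width in a trial of 20 patients and, if the orders turn out unequal, an estimate pulled in a direction set by chance.

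**Working it through.** **The plan's own figure.** Inputs from the power paragraph: partial eta squared 0.205, alpha 0.05, power 0.80, N = 18.
- f = sqrt(0.205/0.795) = 0.5078, as stated.
- With four repeated measures, two groups and lambda = f² × (N − 2) × 3, N = 18 gives lambda = 0.2579 × 48 = 12.38 on 3 and 48 df, and power 0.819. So 18 reproduces, but under settings that the plan does not state.
- If 0.5078 is read as the standardised real-minus-sham difference, a two-sided paired test has power 0.577 at N = 20.

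**Model for the check.** For patient i, d_i = effect − delta + e_i if real comes first, and effect + delta + e_i if sham comes first, with e_i ~ N(0,1). Delta is the session 2 minus session 1 shift in SDs of the paired difference. N = 20, two-sided alpha 0.05.

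**Assumptions not in the documents.**
- Delta lies between 0 and 1 SD.
- The effect is 0.660 SD, chosen because it gives 0.80 power at N = 20. The plan ties 0.80 to 18 subjects at partial eta squared 0.205. I also show 0.5078 SD.

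**Equal orders (10:10).** Power without period is by simulation. Power with period is from the noncentral t on 18 df, with SE = sqrt((1/n1 + 1/n2)/4).

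| Shift (SD) | No period, effect 0.660 | With period | No period, effect 0.5078 | With period |
|---|---|---|---|---|
| 0 | 0.800 | 0.798 | 0.578 | 0.575 |
| 0.25 | 0.78 | 0.798 | 0.55 | 0.575 |
| 0.5 | 0.72 | 0.798 | 0.48 | 0.575 |
| 1 | 0.50 | 0.798 | 0.26 | 0.575 |

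- Interval width without period relative to with period is sqrt(1 + delta² × 20/19) × t19/t18 = 1.03, 1.12 and 1.43 at shifts of 0.25, 0.5 and 1 SD.
- Under no treatment effect, rejection without period is 0.043, 0.029 and 0.006. The test is conservative.

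**Unequal orders.** Bias without period = delta × (n2 − n1)/N, where n1 is the number with real first.
- At 12:8 and delta 0.5: 0.5 × (8 − 12)/20 = −0.10 SD, power 0.57.
- At 8:12: +0.10 SD, power 0.85. With period the estimate is unbiased and power is 0.78 for either split.
- Under no effect at 13:7, rejection without period is 0.065 and 0.076 at shifts of 0.5 and 1 SD.
- The documents state 1:1 but no method. Under simple randomisation, Binomial(20, 0.5) gives 12:8 or worse in 50% of trials and 13:7 or worse in 26%.
- Averaged over simple randomisation, the unadjusted estimate is unbiased and type I error is about 0.05. Power without period is 0.80, 0.78, 0.71 and 0.50 at shifts of 0, 0.25, 0.5 and 1 SD, against about 0.775 with it.

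**RAVLT as treatment by time, 10:10.** A shift that raises T0 and T1 equally cancels, and power stays at 0.80 for shifts up to 1 SD. If the T0-to-T1 gain differs between sessions by 0.25, 0.5 or 1 SD, power is 0.78, 0.72 or 0.50 without period, against 0.80 with it.

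**The case against.** The strongest reply is that the factors come from a sample-size paragraph, so the model actually fitted may well include period. That stands: a reader might infer that the plan has left period out, but the documents leave the model open and prove nothing either way. What remains is that nothing commits the analyst to the term, and the only layout named does not fit one primary outcome.

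Second, randomising the order already protects the comparison. This also stands. A reader might infer that omitting period makes a false positive likely or biases the trial. With equal orders neither is true. With unequal orders the bias is conditional on the split and averages to zero over randomisation. The remaining issue is mainly precision.

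Third, the documents expect the cognitive effect of stimulation to last a few hours, and the sessions are a week apart. That speaks to carryover of stimulation, which is not claimed here. It does not speak to familiarity with a repeated task.

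Fourth, the size of the shift is unknown, and below about 0.1 SD at 10:10, or about 0.25 SD under simple randomisation, adjustment gains nothing. This stands, and is why the point is graded as an improvement.

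Finally, a reader might extend the concern to both primary outcomes equally. The schedule does not support that, because RAVLT has its own T0 in each session.

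**Conclusion.** The point holds as a cheap improvement. As written, the plan does not commit to a model that accounts for session order. If the ANOVA is run with only the factors named, the Face Naming Task comparison and any treatment main effect lose power whenever scores shift between sessions. At 10:10 the loss from 0.80 is about 2 points at a shift of 0.25 SD, 8 at 0.5 SD and 30 at 1 SD. Starting from an effect of 0.5078 SD, the absolute figures are lower and the direction is the same. Both the shift and the 0.660 SD effect are assumptions. The absence of a named period term is certain from the text. The size of the harm is not.

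**What to change.** In the STATISTICAL PLAN, before unblinding, name the model for each primary outcome. For the Face Naming Task score, fit patient, treatment and period (session 1 or 2). For RAVLT, fit the same terms to the T0-to-T1 change. Report the real-minus-sham estimate with a 95% CI.

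If order is instead entered as a between-subject factor in the repeated-measures ANOVA, require Type III (equal-weight) tests of treatment. With unequal orders, a sequential test keeps the order bias while shrinking the error term. Under no treatment effect its rejection rate at shifts of 0.5 and 1 SD is 0.072 and 0.136 at 12:8, and 0.098 and 0.248 at 13:7.

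The change is wording only, with no extra patients, visits or data. If there is no shift, the cost from 0.80 is about 0.2 power points at 10:10 (0.798), about 2 at 12:8 (0.781) and about 4 at 13:7 (0.760). Averaged over simple randomisation it is about 2.5 points (0.774).

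### The 18 subjects for 80% power match a 3-df test over four cells, not a 1-df effect on the stated f(V) scale; if 0.205 describes the 1-df effect, 20 subjects give about 53–58% power

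*Combined protocol and SAP*

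**What the plan says.** The Power analysis paragraph of the STATISTICAL PLAN starts from "an effect size equal to a partial η^2 of 0.205", converts it to f(V) = 0.5078, sets alpha at 0.05 and power at 0.80, and states that "the expected sample size is 18 subjects using a repeated measures ANOVA study with two within-subjects factors". The factors are treatment (real or placebo, by crossover) and time (T0 and T1). It concludes: "The proposed sample size of 20 subjects should be adequate to achieve the main objective of the study".

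On the origin of the effect size it says that "we used data from slightly different studies (both by population and by method of stimulation"). It does not say which effect in those studies gave 0.205, or how many degrees of freedom that effect had. Nor does it name the effect being powered, the number of groups and measurements entered, the within-subject correlation or any sphericity correction. The main analysis is described only as an ANOVA model.

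Two other places bear on this. The opening summary sets up two sequence groups: "Subjects will be randomized in two groups, one receiving a single treatment with gamma tACS (40 Hz) first and the other receiving sham stimulation". END POINTS makes both the Face Naming Task and RAVLT primary. RAVLT is given before and after stimulation, whereas for the other outcome STUDY DESIGN says: "In both sessions, a task, the Face Naming Task, will be carried out during the stimulation with tACS, both real and placebo".

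**The concern.** A within-subject ANOVA with two two-level factors has three effects (treatment, time, treatment by time), each with 1 numerator df. A partial eta-squared of 0.205 on 1 df is a moderate within-subject effect, and 18 subjects is few for detecting it with 80% power. The suspicion was that the calculation had been run for a test with more degrees of freedom than the comparison of real with sham.

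The protocol relies on this figure to call 20 subjects adequate for its main objective. If the figure belongs to another test, readers are promised 80% power when the test of interest may have little better than even odds of finding the assumed effect. A null result could then be misread as evidence that tACS does nothing.

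**Working it through.** **Inputs.** From the Power analysis: partial eta-squared 0.205, f(V) 0.5078, alpha 0.05, power 0.80, treatment and time each with two levels, 18 subjects required, 20 planned. From the opening summary: two sequence groups. The protocol does not say whether sequence is in the model, so both options are shown.

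**Effect-size conversion.** f² = 0.205 / (1 − 0.205) = 0.205 / 0.795 = 0.2579, and f = √0.2579 = 0.5078. The conversion is right.

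**Reproducing 18.** Power is the probability that a noncentral F with noncentrality λ exceeds the 5% critical value of the central F.

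- Four cells treated as one factor (3 df), two groups, df2 = 3(N − 2), λ = 3(N − 2)f²:
  - N = 17: λ = 45 × 0.2579 = 11.60, power 0.789.
  - N = 18: λ = 48 × 0.2579 = 12.38, power 0.819.
  - The smallest N reaching 0.80 is therefore exactly 18. With one group the same formula gives 17; with λ = 3N f² it gives 16.
- 0.5078 entered as an ordinary Cohen f, two measurements, zero correlation, F(1, N − 1), λ = 2N f²: power 0.794 at N = 17 and 0.819 at N = 18. This also gives 18, but it contradicts the f(V) label and uses two measurements where the stated design has four cells.

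**The stated design.** Each effect has 1 df and is tested against its own error term. Assume 0.205 is the partial eta-squared of that effect.

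| Convention | Power, N = 18 | Power, N = 20 | First N with power ≥ 0.80 | f (partial eta-squared) giving 0.80 at N = 20 |
|---|---|---|---|---|
| df2 = N − 1, λ = N f² | 0.5288 | 0.5775 | 33 | 0.660 (0.304) |
| df2 = N − 1, λ = (N − 1)f² | 0.5060 | 0.5561 | 34 | 0.678 (0.315) |
| Sequence in model, df2 = N − 2, λ = N f² | 0.5257 | 0.5750 | 33 | 0.663 (0.305) |
| Sequence in model, df2 = N − 2, λ = (N − 2)f² | 0.4797 | 0.5315 | 35 | 0.698 (0.328) |

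The choice of convention moves the answer by two subjects. It does not bring it near 18.

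**If 0.205 is instead the 3-df omnibus effect.** At N = 20 the total noncentrality is 3 × 18 × 0.2579 = 13.92. Power for a single contrast then depends on how that total is spread.

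- Only the real, post-stimulation cell differs, by d: treatment, time and interaction each take d²/4 of the total 3d²/4, so each has λ = 13.92 / 3 = 4.64. Power is 0.53 with its own error (18 df) or 0.56 with pooled error (54 df).
- The whole effect is time: power for treatment by time is 0.05.
- The whole effect lies in the contrast of interest: power is 0.94.
- Power of 0.80 needs 63% of the effect in that contrast (58% with pooled error).

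**What the omnibus test responds to.** In 20,000 simulated trials with N = 20, a time effect only and total λ = 13.92, the 3-df test was significant in 87.3%. The treatment-by-time test was significant in 5.0%.

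**Fit to the primary outcomes.** RAVLT has T0 and T1 in each session, so the 2×2 layout applies. The Face Naming Task is described only during stimulation. That gives one measurement per session and no time factor, so the powered design is not the one described for that outcome.

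**The case against.** The strongest reply is that the settings behind 18 are not stated, so its 3-df origin is an inference. The match is exact only with two groups entered, and one 1-df calculation, with an ordinary Cohen f, also gives 18. The origin is indeed inferred, and the statement that no 1-df effect gives 18 holds only on the stated f(V) scale. The Cohen f route does not rescue the paragraph, because it conflicts with the f(V) label and with the four-cell design.

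Second, 53–58% depends on what 0.205 describes, and the source studies are not available here. This also stands: the figure is conditional. If 0.205 is an omnibus effect, power for the contrast could lie anywhere from 0.05 to 0.94.

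Third, the protocol does not state its error term. Testing a 1-df effect against a pooled within-subject error, with df2 = 3(N − 1) and λ = 3(N − 1)f², would need only 12 subjects and give power 0.96 at 20. That is not the usual analysis of a two-factor repeated-measures design, and it does not give 18 either. Effect-specific error is nonetheless an assumption and should be stated.

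Fourth, the low end of the range needs sequence in the model, which the power sentence does not mention. Without it the range is 0.556–0.577 at 20 subjects, with 33–34 needed. This narrows the range but leaves the shortfall in place.

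Finally, the timing of the Face Naming Task is a separate gap and does not decide whether 18 is right. It does matter when the powered effect is named for each outcome.

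**Conclusion.** The concern holds. The effect-size conversion is correct, but 18 subjects for 80% power does not follow for any effect of the stated 2×2 within-subject ANOVA, taken on the f(V) scale with each effect tested against its own error. About 33–35 subjects would be needed, nearly double the stated number, and the planned 20 give about 53–58% power. These figures assume that 0.205 is the partial eta-squared of the 1-df effect of interest, at two-sided alpha 0.05.

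That 18 fails to follow is certain on that scale. That it came from a 3-df four-cell setting is the best-fitting explanation, not a documented fact, and the conclusion does not depend on it. Reading 0.205 as an omnibus effect does not secure 80% either, unless about 58–63% of the effect falls in the contrast of interest, and the protocol offers nothing to support that. This should be corrected.

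**What to change.** Rewrite the Power analysis paragraph as follows.

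1. Name the powered 1-df effect for each primary outcome: treatment by time for RAVLT, and real against sham for the Face Naming Task if it is measured only during stimulation.
2. State that a partial eta-squared of 0.205 is assumed for that effect, and say which effect in the source studies gave the value and on how many df.
3. Replace the sample-size claim with, for example: *20 subjects give about 53–58% power for a partial eta-squared of 0.205, and 80% power for a partial eta-squared of about 0.30–0.33 (f about 0.66–0.70).* This sentence is true for any 1-df effect tested against its own error.
4. State the error term, the noncentrality convention and whether sequence is in the model, so that one figure can replace the range.
5. Remove the claims that 18 subjects give 80% power and that 20 are adequate for the assumed effect.

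The cost is one reworded paragraph. Enrolment, endpoints and procedures are unchanged. The drawback is that the stated power looks less favourable.
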